1.2 Secondary Objectives

- b. To assess whether daily duloxetine decreases worst joint pain in women with AIMSS, as measured at 12 weeks by the modified BPI-SF.
- c. To assess whether daily duloxetine decreases pain interference in women with AIMSS, as measured at 12 weeks by the modified BPI-SF.

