10.2 Main Secondary Outcome

Reduction in worst joint pain according to the BPI-SF worst pain score (item #2) at 12 weeks. This item has a scale of 0 to 10 with 0 indicating “No pain” and 10 indicating “Pain as bad as you can imagine”.

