The primary analysis will rely on longitudinal measures of BPI at Weeks 2, 6, and 12 for improved power. (Thus the proportion of patients with zero follow-up observations will likely be less than the specified 5% non-adherence and 15% dropout at 12 weeks used for power calculations.) Assessment windows of +/- 7 days, +/- 14 days, and +/- 14 days will be allowed for the 2, 6, and 12 week timepoints. (Given the primary analysis is based on longitudinal measures, a sensitivity analysis will consider all observations within 14 weeks of registration.) The analysis will be performed using mixed models, adjusted for baseline average pain and the stratification factors. To minimize missed assessments, SWOG utilizes an electronic system to remind institutions in real-time that patients are due for follow-up assessment. If the proportion of missing follow-up data is >20% (the sum of the specified targets for non-adherence and dropout), plots of mean pain levels over time for patients grouped by number of follow-up responses will be examined to check for patterns of informative missing data. Should these plots suggest that data may not be missing at random, pattern mixture models, which models missingness patterns through stratification, will be utilized for analysis of the longitudinal BPI pain data. [\(48, 49\)](#)

Under the intention-to-treat principle, the primary analysis will be based on all eligible, randomized patients. To allow for an ineligibility rate of 8%, as found on our recent Symptom Control study [S0715](#), a total of 294 patients will be enrolled to achieve 270 eligible patients.

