11.3 Secondary Endpoints

The following secondary analyses will be conducted:

- a. Multiple linear regression analyses of the individual assessment timepoints will be conducted to identify potential critical effectiveness timepoints and to allow comparisons to other studies. These analyses will include the baseline score (as a covariate) as well as the pre-specified stratification factors.
- b. At weeks 2, 6, and 12, we will investigate whether duloxetine 60 mg daily:
 1. Decreases worst joint pain according to the BPI.
 2. Improves functioning, pain, and stiffness in the knees/hips according to the Western Ontario and McMaster Universities Osteoarthritis (WOMAC) scale. Differences between the two study arms of at least two points on the WOMAC Index are of interest. [\(50, 51\)](#) We will also evaluate clinically meaningful change for the WOMAC Index with respect to the $\frac{1}{3}$ to $\frac{1}{2}$ standard deviation during the study period of 12 weeks.
 3. Improves function, pain and stiffness in the hands according to the Modified Score for the Assessment and Quantification of Chronic Rheumatoid Affections of the Hands (M-SACRAH). Differences between the two study arms of at least two points on the M-SACRAH are of interest. [\(50,51\)](#) We will also evaluate clinically meaningful change for the M-SACRAH with respect to the $\frac{1}{3}$ to $\frac{1}{2}$ standard deviation during the study period of 12 weeks.
 4. Improves functional quality of life as measured by the Functional Assessment of Cancer Therapy-Endocrine Scale (FACT-ES).[\(52,53\)](#) Trial Outcome Index (TOI). Clinically meaningful change in FACT-ES TOI scores will also be based on $\frac{1}{3}$ to $\frac{1}{2}$ of a standard deviation. [\(53-55\)](#)
 5. Improves the proportion of patients reporting changes for the better versus worst as measured by the Global Rating of Change Scale. The GRCs for joint pain and for joint stiffness will be used to identify patients who report they are worse (combining scores of -1 through -3), the same score (score of 0), or better (combining scores of +1 through +3) since the last time they completed the questionnaire. [\(54-56\)](#) Mean scores for the WOMAC Index, BPI, M-SACRAH, and FACT-ES TOI will be compared for groups based on those patients who select “a little better” and “a little worse” on the GRC ratings to identify minimally important change. [\(54-56\)](#)

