6. Reduces depression as measured by the Patient Health Questionnaire (PHQ-9). Differences between the two arms of at least five points on the PHQ-9 at 12 weeks will be of interest. (57) Clinically meaningful change in PHQ-9 scores will also be based on $\frac{1}{3}$ to $\frac{1}{2}$ of a standard deviation. (57)
 7. Decreases analgesic use.
 8. Increases adherence to, and reduces the discontinuation rate for, AI therapy.
 9. Affects measures of pain interference.
 10. Reasons for treatment discontinuation will also be described.
- c. Interaction tests between treatment and stratification variables will be conducted to explore whether these factors are predictive of average pain scores.
 - d. A logistic regression analysis of responders will be conducted, where a response to intervention is defined as a reduction of 2 or more points in average pain according to the BPI. (50)
 - e. In addition, we will explore the relationship between the severity of arthralgias and degree of benefit from therapy in each of the treatment groups and inherited variants in genes responsible for duloxetine metabolism and activity (COMT, HTR3A, SLC6A2, SLC6A4, CYP1A2, CYP2D6) and aromatase (CYP19A1). Finally, we will explore the relationship between baseline and change in serum inflammatory cytokine levels with 12 weeks of treatment and the degree of benefit from therapy in each of the treatment groups.

For linear scales, secondary endpoints will be analyzed using multiple linear regression analyses including the baseline score as a covariate and the pre-specified stratification factors. For binary outcomes, logistic regression will be used.

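### The Week-12 analyses of worst pain and pain interference could use the Week-2 and Week-6 scores of patients with no Week-12 score; a mixed model would do this at little cost

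*Combined protocol and SAP*

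**What the plan says.** Section 10.2 defines the main secondary outcome as "Reduction in worst joint pain according to the BPI-SF worst pain score (item #2) at 12 weeks". Section 1.2 adds a second objective at the same time: "To assess whether daily duloxetine decreases pain interference in women with AIMSS, as measured at 12 weeks by the modified BPI-SF".

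Section 11.3b opens "At weeks 2, 6, and 12, we will investigate whether duloxetine 60 mg daily" and lists worst pain as item 1 and pain interference as item 9. The closing rule of 11.3 sets the model: "For linear scales, secondary endpoints will be analyzed using multiple linear regression analyses including the baseline score as a covariate", with the stratification factors added. Section 11.3a describes the same kind of analysis: "Multiple linear regression analyses of the individual assessment timepoints will be conducted to identify potential critical effectiveness timepoints". Section 11.3 names no repeated-measures model and no imputation.

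For average pain, Section 11.1 takes another route: "The primary analysis will rely on longitudinal measures of BPI at Weeks 2, 6, and 12 for improved power". It specifies the model: "The analysis will be performed using mixed models, adjusted for baseline average pain and the stratification factors". It also expects that "the proportion of patients with zero follow-up observations will likely be less than the specified 5% non-adherence and 15% dropout at 12 weeks" used in the power calculation.

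**The concern.** A regression on one visit uses only patients with a score at that visit. The plan does not say that patients are left out; this follows from a single-visit regression with no imputation. Worst pain and pain interference come from the same BPI-SF, completed at the same visits as average pain. The plan's own reason for using all three visits for average pain therefore applies to them too, and the plan gives no reason for treating them differently.

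Two things are at stake for the Week-12 estimates. One is some precision. The other is protection if the chance of missing Week 12 is related to pain already recorded at Week 6 and that relation, or the loss rate, differs between arms.

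**Working it through.** **Plan's figures (Section 11.1).** With two-sided alpha 0.05, 80% power, SD 2.3 and difference 1.0, n per arm = 2(1.960 + 0.842)² × 2.3² / 1.0² = 83.0 (stated: 83). For the diluted difference of 0.85, 83.0 / 0.85² = 114.9, so 115 per arm and 230 in total. Then 230 / 0.85 = 270.6 (stated: 270). These reproduce.

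**Patients not used.** 15% of 270 is 40.5, which leaves about 229.5 patients in the Week-12 regression.

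**Precision if loss is random.** Ignoring baseline, the completers' standard error is 2.3 × √(2/114.75) = 0.304, and power at 0.85 is Φ(0.85/0.304 − 1.96) = 79.9%. Suppose all lost patients have Weeks 2 and 6, and visits correlate equally at ρ. Weeks 2 and 6 then explain R² = 2ρ²/(1 + ρ) of the Week-12 variance, and

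effective N = 1 / [(1 − R²)/229.5 + R²/270].

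- ρ = 0.3: R² = 0.138, effective N = 234, power 80.8%.
- ρ = 0.5: R² = 0.333, effective N = 242, power 81.9%.
- ρ = 0.8: R² = 0.711, effective N = 257, power 84.2%.

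If only a third of lost patients have both visits and a third have Week 2 alone, ρ = 0.3 gives 232 and 80.4%. The gain is about 0.5 to 4 points. The correlations are assumptions; the documents give none.

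**Bias if loss is not random.** If patients with more Week-6 pain are likelier to miss Week 12, the completers' Week-12 mean shifts in each arm. Equal shifts cancel in the arm difference; unequal shifts do not. The size was simulated with 4,000 trials per setting.

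- *From the documents:* 135 per arm, SD 2.3 (also the pilot's worst-pain SD at 8 weeks, Section 2.0, Table 1), true difference 0.85 (Section 11.1, for average pain), 15% missing.
- *Assumed:* correlation 0.5 to 0.7 between follow-up visits and 0.4 with baseline; log-odds of a missing Week-12 score 0.2 to 0.6 per Week-6 point, halved in the other arm where dependence is called twice as strong.
- *Comparator:* the maximum-likelihood equivalent of an unstructured mixed model with treatment-by-visit terms, with only Week 12 missing.

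Baseline adjustment brings the standard error to about 0.304 × √(1 − 0.4²) = 0.28.

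| Loss pattern | Regression estimate | Distance from 0.85 |
|---|---|---|
| Random, or equal dependence at equal rates | 0.84–0.86 | none beyond simulation error |
| One rule in both arms (placebo loses 16–18%, duloxetine 12–14%) | 0.79–0.85 | 0.00–0.06, toward no effect |
| Twice as strong in placebo | 0.76–0.82 | 0.03–0.09, toward no effect |
| Twice as strong in duloxetine | 0.88–0.94 | 0.03–0.09, away from no effect |

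The model gives 0.84–0.86 throughout. The largest distance in the table is 0.09 / 0.28 = 0.32 of a standard error. Power is 85–87% for the regression against 86–89% for the model in the first row, and 82–86% against 87–89% in the second.

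**Sensitivity, with dependence twice as strong in placebo.** At 10% missing the regression gives 0.78–0.84, and at 5% missing 0.82–0.84. Widening the correlations to 0.4 and 0.8 gives 0.75–0.83. With no true effect the regression rejects 4.8–6.6% of the time and the model 4.3–5.4%. In an extreme case, with dependence in placebo only, the regression gives 0.64–0.80.

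**Where the model does not help.** If all loss comes before Week 2 and depends on unobserved Week-2 pain in placebo, both methods give 0.71.

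**The case against.** A baseline-adjusted regression at the objective's own time point is a recognised, pre-specified method that estimates the Week-12 difference directly. Section 11.3a gives single-visit analyses a purpose: finding critical time points and comparing with other studies. A mixed model for the primary does not make a simpler secondary analysis wrong. All of this stands, and it is why the point is an improvement and not a correction.

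The 15% is a planning allowance for dropout, not a forecast of missing questionnaires. Questionnaires continue after treatment stops (Section 7.4; Section 9.0 footnotes), a telephone interview follows a missed visit (Section 15.2b), and sites receive reminders and a 14-day window either side of Week 12 (Section 11.1). This stands too: 40 is an upper figure. These measures reduce loss but do not say how the remaining loss is analysed. The pattern-mixture fallback sits in Section 11.1, under the primary objective, and starts only above 20% missing.

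The simulation favours the model: every lost patient has Weeks 2 and 6, and the data are missing at random. Correlations and loss patterns come from outside the documents, and pain interference was not simulated. These limits are accepted.

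A reader might infer that the regression is unbiased only if loss has nothing to do with interim pain. That is too strong, because equal dependence at equal rates leaves it essentially unbiased. Nor are Week-2 and Week-6 scores discarded: they enter their own visits' regressions. Nor is comparison with the primary lost: Section 11.3a, read as covering average pain, gives a like-for-like Week-12 regression.

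**Conclusion.** The point holds as a low-cost improvement, not as an error in the plan. On the text, patients without a Week-12 score (at most about 40 of 270) do not contribute to the Week-12 estimates of worst pain and pain interference, even where their Week-2 and Week-6 scores exist.

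The regression is guaranteed unbiased, if correctly specified, when loss depends only on arm, baseline score and stratification factors. It can be biased when dependence on interim pain or loss rates differ by arm. The size is then about 0 to 0.09 points on a true 0.85, up to about a third of a standard error, and less at 5–10% missing. With no bias, the model gains about 1 to 4 points of power (half a point at the lowest correlation tried).

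These sizes apply to worst pain with average-pain inputs as a stand-in. For pain interference the pilot's 8-week SD was smaller (1.3, Section 2.0, Table 1), so a bias in points would probably be smaller.

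A reader might go further and conclude that the main secondary result is unreliable or leans one way. The documents do not support that: they give no expected loss pattern, the direction is unknown, and the placebo-only case is an assumed extreme. The primary analysis is unaffected.

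**What to change.** In Section 11.3, make a repeated-measures mixed model on Weeks 2, 6 and 12 the main analysis of BPI worst pain and pain interference. Include treatment, visit, treatment-by-visit, baseline score, stratification factors and an unstructured covariance, and take the Week-12 treatment contrast as the estimate. Keep the single-visit regressions, including 11.3a, as supportive analyses.

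The cost is a wording change and slightly more analysis work, with no new data and no change in sample size. The estimates then rely on missing at random and on the covariance model. Patients with no follow-up score are still not recovered. Early loss would be such a case: in the pilot, most stopping for adverse events came within a few days of starting (Section 2.0), although stopping treatment is not the same as missing questionnaires.

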1.3 Additional Exploratory Objectives

- d. To investigate whether daily duloxetine improves functioning, pain, and stiffness in the knees/hips according to the Western Ontario and McMaster Universities Osteoarthritis (WOMAC) scale;
- e. To investigate whether daily duloxetine improves function, pain and stiffness in the hands according to the Modified Score for the Assessment and Quantification of Chronic Rheumatoid Affections of the Hands (M-SACRAH);
- f. To investigate whether daily duloxetine improves functional quality of life as measured by the Functional Assessment of Cancer Therapy-Endocrine Scale (FACT-ES);
- g. To investigate whether daily duloxetine improves the proportion of patients reporting changes for the better versus worst as measured by the Global Rating of Change Scale;
- h. To investigate whether daily duloxetine improves/decreases analgesic use;
- i. To investigate whether daily duloxetine improves/increases adherence to, and reduces the discontinuation rate for, aromatase inhibitor (AI) therapy.
- j. To assess whether patients receiving duloxetine as compared to placebo have improved depression as measured by the Patient Health Questionnaire (PHQ-9) at Weeks 6 and 12 (for patients experiencing depression at baseline).
- k. To explore the relationship between inherited variants in genes responsible for duloxetine metabolism and activity (COMT, HTR3A, SLC6A2, SLC6A4, CYP1A2, CYP2D6) and aromatase (CYP19A1) and change in pain with 12 weeks of treatment.
- l. To explore the impact of treatment on serum inflammatory cytokine levels with 12 weeks of treatment at baseline and 12 weeks.
- m. To bank blood samples for future correlative analyses.

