7.2 Study Plan

a. Initial Visit

Before beginning the intervention, patients will have a general physical exam (including recording of weight and height) and a mandatory blood draw for whole blood and serum (see [Section 15.1](#)). The patient will complete the **S1202** Brief Pain Inventory–Short Form (BPI-SF) prior to registration to confirm eligibility (see [Section 5.2d](#)). Patients will complete the following questionnaires prior to beginning treatment with blinded study drug:

S1202 Western Ontario and McMaster Universities Osteoarthritis (WOMAC) Index (Version 3.1)

S1202 Modified-Score for the Assessment and Quantification of Chronic Rheumatoid Affections of the Hands (M-SACRAH)

S1202 FACT – ES Trial Outcome Index (Version 4)

S1202 Patient Health Questionnaire-9 (PHQ-9)

It should take the patient about 20-25 minutes to complete the questionnaires. See [Section 15.2](#) for instructions for administration of the questionnaires.

The nurse or CRA must complete the **S1202** Cover Sheet for Patient-Completed Questionnaires.

Bottle #1 and #2 are dispensed at this visit. Patients will take 1 capsule daily for the first 7 days, then increase the dose to 2 capsules daily. The dose that should be taken each day should be listed on the patient calendar (see [Section 15.2c.1](#)).

b. Follow-up Visits

Follow-up visits will occur on Day 15, 43, 85, and 169 after start of treatment. Drug adherence will be ascertained by the nurse or CRA by review of the patient completed **S1202** Intake Calendar on Day 15, 43, and 85, as well as count of blinded drug capsules on the Day 43 and 85 visits. After the Day 85 pill count, the nurse or CRA must dispense bottle #3 to the patient to complete the Day 85 to Day 91 taper. Counts of blinded drug capsules remaining should be recorded on the **S1202** Treatment Form and the patient's medical record through the Day 85 visit. Adherence to AI should be recorded on the **S1202** Treatment Form at every visit. Adverse events will be assessed and recorded on the **S1202** Adverse Event Summary Form through the Day 85 visit. Use of pain medications, steroids, physical therapy, and acupuncture will be recorded on the **S1202** Supplemental Agents Reporting Form.

The nurse or CRA will contact the patient by telephone on Day 99 to assess adverse events following study drug discontinuation. Adverse events will be recorded on the **S1202** Adverse Event Summary Form

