8.2 General Considerations

Patients who are taking narcotics, tramadol, gabapentin, and/or pregabalin at study registration should continue to take a stable dose of medication or should decrease their dose during study participation, as tolerated. Dose increases for these medications should be discouraged.

Patients who need additional analgesic medication during study participation are requested to take acetaminophen. Patients should not undergo therapy with other treatment modalities such as physical therapy, acupuncture, systemic steroids, or intra-articular steroid injections during study participation unless medically necessary. Usage of all medications and other therapies for treatment of pain should be documented on the **S1202** Supplemental Agents Reporting Form.

Caution should be taken if patients take aspirin or non-steroidal anti-inflammatory drugs during study participation because of the increased risk of bleeding when these medications are used in combination with duloxetine.

Caution should be taken if patients take triptan medications, tramadol, linezolid, or other serotonergic medications during study participation because of the increased risk of serotonin syndrome when these medications are used in combination with duloxetine.

Duloxetine has been associated with an increased risk of suicide. Therefore, at the day 43 and 85 study visits, the answer to question #9 on the PHQ-9 should be reviewed before the patient leaves the clinic. In addition, all patients should be asked about suicidal thoughts or actions at the Day 15 study visit and Day 99 telephone call. If a patient reports suicidal thoughts or actions, or answers anything other than "Not at all" to question #9, the treating physician should be immediately notified.

NOTE: Concomitant therapy with heparin and warfarin is not permitted while on study treatment.

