14.4 Data Submission Overview and Timepoints

- a. AFTER REGISTRATION BUT PRIOR TO BEGINNING PROTOCOL TREATMENT:

Submit baseline whole blood for DNA and blood for serum biomarkers as outlined in [Section 15.1](#). The SWOG Specimen Tracking System must be used for specimen submission.

- b. WITHIN 7 DAYS OF REGISTRATION:

Submit the following:

S1202 Onstudy Form

S1202 Cover Sheet for Patient-Completed Questionnaires

S1202 Brief Pain Inventory Short Form (BPI-SF)

S1202 Western Ontario and McMaster Universities Osteoarthritis (WOMAC) Index (Version 3.1)

S1202 Modified-Score for the Assessment and Quantification of Chronic Rheumatoid Affections of the Hands (M-SACRAH)

S1202 FACT-ES Trial Outcome Index (Version 4)

S1202 Patient Health Questionnaire-9 (PHQ-9)

Institutional surgical pathology report to confirm diagnosis of ER/PgR status

c. WITHIN 14 DAYS OF DAY 15, 43, 85 STUDY ASSESSMENTS:

Submit the following:

S1202 Treatment Form

S1202 Adverse Event Summary Form

S1202 Supplemental Agents Reporting Form

S1202 Cover Sheet for Patient-Completed Questionnaires

S1202 Brief Pain Inventory Short Form (BPI-SF)

S1202 Western Ontario and McMaster Universities Osteoarthritis (WOMAC) Index (Version 3.1)

S1202 Modified-Score for the Assessment and Quantification of Chronic Rheumatoid Affections of the Hands (M-SACRAH)

S1202 FACT-ES Trial Outcome Index (Version 4)

S1202 Global Ratings of Change in Joint Pain and Stiffness

d. WITHIN 14 DAYS OF DAY 43 AND 85 ASSESSMENTS:

In addition to the forms listed in [Section 14.4c](#), submit the **S1202** Patient Health Questionnaire-9 (PHQ-9)

e. WITHIN 14 DAYS OF DAY 85 ASSESSMENT:

In addition to the forms listed in [Sections 14.4c](#) and [14.4d](#), submit the **S1202** Patient Treatment Satisfaction Form

f. AT THE DAY 85 STUDY ASSESSMENT:

Submit blood for serum biomarkers as outlined in [Section 15.1](#). The SWOG Specimen Tracking System must be used for specimen submission.

g. WITHIN 14 DAYS OF THE DAY 99 TELEPHONE CALL TO PATIENT:

Submit the **S1202** Adverse Event Summary

h. WITHIN 14 DAYS OF THE DAY 169 FINAL STUDY ASSESSMENT:

Submit the following:

S1202 Supplemental Agents Reporting Form

S1202 Cover Sheet for Patient-Completed Questionnaires

S1202 Brief Pain Inventory Short Form (BPI-SF)

S1202 Western Ontario and McMaster Universities Osteoarthritis (WOMAC) Index (Version 3.1)

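### No baseline recording of NSAID or acetaminophen use is described, so the analgesic-use comparison, though valid, is post-baseline and unadjusted as planned

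*Combined protocol and SAP*

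**What the plan says.** Objective 1.3h is "To investigate whether daily duloxetine improves/decreases analgesic use". Section 11.3b.7 repeats it as "Decreases analgesic use", among the analyses at Weeks 2, 6 and 12. Neither place gives a unit, a drug list, a look-back period or an outcome type.

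Section 11.3 closes with two model statements. The first is "For linear scales, secondary endpoints will be analyzed using multiple linear regression analyses including the baseline score as a covariate", together with the stratification factors. The second is "For binary outcomes, logistic regression will be used", with no baseline term named.

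On data collection, Section 7.2b (Follow-up Visits) says: "Use of pain medications, steroids, physical therapy, and acupuncture will be recorded on the" S1202 Supplemental Agents Reporting Form. Section 14.4c, headed "WITHIN 14 DAYS OF DAY 15, 43, 85 STUDY ASSESSMENTS", is the first scheduled submission of that form. Sections 14.4h, 14.4i and 14.4k add Day 169, removal from intervention, and death on intervention.

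Section 8.2 asks patients who need extra analgesia to use acetaminophen, and it allows aspirin and NSAIDs with caution.

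**The concern.** The question is about a decrease, but the form that would show the starting level does not appear before treatment. Some baseline analgesic use is to be expected. Patients enter with average pain of at least 4 (5.2d), Section 2.0 describes current management as oral analgesics and exercise, and Section 5.0 requires no washout of acetaminophen or NSAIDs. Randomisation is balanced on baseline pain and prior taxane use only (6.0), so a chance imbalance in analgesic use could arise and would be neither visible nor correctable.

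There is also a smaller effect on reading the pain results. Without a starting record, pain treatment that is new or increased on study may look the same as treatment that simply continued. Baseline use cannot be reliably reconstructed once treatment has begun.

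**Working it through.** **1. Where the form is required.** This comparison uses the text lists. The calendar in 9.0 is weak evidence, because its pre-study marks are missing from the extract; even the Onstudy Form row shows none.

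| Place | Supplemental Agents form listed? |
|---|---|
| 7.2a Initial Visit | No |
| 14.4b, "WITHIN 7 DAYS OF REGISTRATION" | No. It lists the Onstudy Form, Cover Sheet, five questionnaires and pathology report |
| 7.2b Follow-up Visits | Yes |
| 14.4c Days 15, 43, 85 | Yes (first occurrence) |
| 14.4h, 14.4i, 14.4k | Yes |

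**2. Other baseline sources.** The only candidate is the Onstudy Form. The Revision 1 memorandum says its other-treatment questions were updated to match Section 5.0. In Section 5.0, criterion 5.2l covers gabapentin, pregabalin, tramadol and narcotics, and 5.2h mentions aspirin as permitted. Neither acetaminophen nor NSAIDs as a class appear. The documents therefore describe no baseline record of them.

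**3. Could Day 15 stand in?** Not well. It falls after two weeks of blinded drug (7.1). In the open-label pilot (Section 2.0, Table 1), mean average pain had gone from 5.5 at baseline to 2.5 at 2 weeks, a fall of 3.0 points. A covariate measured then may already carry part of the treatment effect.

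**4. What can still be tested.** The plan gives no figure for analgesic use, so its evaluable number from 11.1 is borrowed. With SD 2.3, difference 0.85, two-sided 0.05 and 80% power, n per arm = 2 × (2.3 × 2.802)² / 0.85² = 83.04 / 0.7225 = 114.9. This rounds up to 115 and reproduces the plan's 230 in total.

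- *Numeric outcome, unadjusted.* Detectable standardised difference = 2.802 × √(2/115) = 0.37 SD.
- *Yes/no outcome, unadjusted.* At assumed placebo use of 30%, 50% or 70%, the detectable drop at 80% power is about 15, 18 or 18 percentage points (two-proportion normal approximation, variance pooled under the null).

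**5. What a baseline covariate would add, numeric outcome only.** Residual variance is multiplied by 1 − r², where r is the correlation of baseline with follow-up use. The documents give no value of r; the values below are assumptions.

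| r | 1 − r² | Variance removed | Equivalent sample factor 1/(1 − r²) | Detectable difference |
|---|---|---|---|---|
| 0.3 | 0.91 | 9% | 1.10 | 0.35 SD |
| 0.5 | 0.75 | 25% | 1.33 | 0.32 SD |
| 0.7 | 0.51 | 49% | 1.96 | 0.26 SD |

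**The case against.** The strongest reply is that randomisation already answers the question. Comparing post-baseline use between arms is valid without any baseline value, and it shows whether duloxetine lowers use relative to placebo. That stands. What is lost is precision, correction of chance imbalance and within-patient change.

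Three stronger readings are tempting, and the documents do not support them.

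- *A reader might infer that the planned model cannot be fitted.* The baseline-adjusted regression is stated for linear scales, and analgesic use is never defined as one. Scored as any use, yes or no, it falls under the logistic sentence, which needs no baseline. Only a numeric score, or a binary outcome such as reduced or stopped, would need one.
- *A reader might infer that no baseline exists.* The Onstudy Form and the Supplemental Agents form are not in the documents. Either could ask about prior use, start dates or dose changes. What can be said is that no baseline collection is described.
- *A reader might infer that the stable-dose rule in 8.2 ("Dose increases for these medications should be discouraged") cannot be checked.* That rule covers only the drugs in 5.2l, for which sites must already confirm 30 days of stable dosing before registration.

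It is also fair to say that the missing definition of the variable is the more basic gap, since it decides which model applies. The fix should include it.

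**Conclusion.** The point holds as a minor, cheap improvement. No baseline collection of NSAID or acetaminophen use is described, although these include the drugs whose use is most free to change under 8.2. The analysis in 11.3b.7 remains a valid post-baseline contrast between arms. As described, it does not support a statement about decrease within patients or an adjustment for starting use.

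The effect is confined to an exploratory objective (1.3h) and, to a lesser degree, to describing new or increased pain treatment alongside the pain results. The primary analysis and its sample size (270 eligible, 294 enrolled) are unchanged. The precision figures rest on assumed correlations and on a numeric outcome that the plan does not specify. They illustrate a possible gain and do not measure a shortfall.

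**What to change.** 1. Add one completion of the S1202 Supplemental Agents Reporting Form before the first capsule to 7.2a, 14.4b and the pre-treatment column of 9.0. It should cover drug, dose, days of use in the past 7 days and non-drug pain therapy.
2. In 11.3b.7, define the analgesic-use variable: which drugs count, over what look-back period, and whether it is numeric or yes/no.
3. Include the baseline value of that variable as a covariate in the matching linear or logistic model, and use the same record as the reference for new or increased pain treatment.
4. If a baseline cannot be collected, or for patients already treated, state that the comparison is post-baseline only and word the objective as a between-arm difference in use.

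The cost is a few minutes of staff time per patient on an existing form, plus short text changes in 7.2a, 9.0, 14.4b and 11.3. Patients complete no extra questionnaire, and the sample size does not change.
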